9.3.2. Safety Analyses

Adverse events will be coded using the Medical Dictionary for Regulatory Activities (MedDRA) version 18.0 or higher and will be graded according to the NCI-CTCAE, v 4.03 or higher.

Summaries of AEs will be based on TEAEs. A TEAE is an AE that emerges or worsens in the period from the first dose of study treatment etigilimab or nivolumab, whichever is earlier, to 100 days after the last dose of etigilimab or nivolumab (whichever is dosed last) or until starting another treatment.

TEAEs will be summarized by treatment group and by the frequency of subjects experiencing TEAEs corresponding to MedDRA system organ classes and preferred terms.

Separate tabulations will also be produced for TEAEs assessed as related to study drug(s), TEAEs that led to treatment discontinuation, TEAEs that led to death, and TEAEs \geq Grade 3 in severity. Treatment-emergent serious AEs and SAEs related to study drug(s) will also be tabulated.

Laboratory results (hematology, serum or plasma chemistry, and coagulation) and the corresponding change from baseline values will be summarized by group and scheduled timepoint. A shift table, tabulation for baseline to each scheduled assessment and the worst post treatment value according to the CTCAE grade, will be provided for selected clinical laboratory tests. Laboratory results together with the normal ranges and CTCAE grade will be listed. Laboratory values that are below or above the normal ranges will be flagged.

Vital signs and ECGs and the corresponding changes from baseline will be summarized by group and scheduled timepoint.

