10.11. Safety Analysis

All analyses of safety endpoints will be descriptive and will use the Safety Analysis Set. No formal statistical analysis of safety data will be performed.

10.11.1. *Adverse Events*

Adverse event (AE) data presentations will be produced for adverse events that occur during the study.

All adverse events will be coded using MedDRA, Version 26.0.

An adverse event is defined as treatment emergent if the onset date is on or after the date of first dose of study drug up to 100 days after the last dose of study drug and before starting any subsequent cancer treatment. Should any onset date for an adverse event be missing or only a partial date recorded (such that it cannot be determined if the event onset was prior to the date of first dose) then it will be assumed that the event is treatment emergent, unless the adverse event stop date indicates otherwise. Any adverse event with an onset date earlier than the date of first dose of study drug will be classified as a pre-treatment adverse event and will be identified in subject listings only.

A summary of treatment-emergent AEs will be presented by cohort showing the number of subjects with events (also split by severity; mild, moderate, severe), number of subjects with SAEs, number of subjects with related events and number of subjects with events leading to early withdrawal from the study.

Additionally, each of the summaries below will be presented for treatment emergent AEs:

- Adverse Events by cohort, System Organ Class (SOC) and Preferred Term (PT).
- Adverse Events by cohort, SOC, PT and severity.
- Adverse Events related to study drug by cohort, SOC and PT:
 - etigilimab
 - nivolumab
 - etigilimab and nivolumab
 - etigilimab or nivolumab
- Serious Adverse Events by cohort, SOC and PT.
- Serious Adverse Events related to study drug by cohort, SOC and PT:
 - etigilimab
 - nivolumab
 - etigilimab and nivolumab
 - etigilimab or nivolumab
- Adverse Events that led to death by cohort, SOC and PT.
- Adverse Events that led to treatment discontinuation by cohort, SOC and PT.
- Adverse Events that led to withdrawal from the study by cohort, SOC and PT.
- Adverse Events of Grade 3 or Higher by cohort, SOC and PT.
- Adverse Events of Special Interest by cohort, SOC and PT:

- Infusion Related Adverse Events
- Immune Related Adverse Events
- Infusion or Immune Related Adverse Events

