13.2. List of Tables

Table Number	Table Title
14.1.1	Participant Disposition – All Subjects
14.1.2.1	Demography – Safety Analysis Set
14.1.2.2	Demography of Cohort F – Safety Analysis Set
14.1.3.1	Baseline Disease Characteristics – Safety Analysis Set
14.1.3.2	Baseline Disease Characteristics of Cohort F – Safety Analysis Set
14.1.4.1	Prior Cancer Treatments – Safety Analysis Set
14.1.4.2	Other Prior Medications – Safety Analysis Set
14.1.4.3	Concomitant Medications – Safety Analysis Set
14.1.5	Investigational Product Exposure – Safety Analysis Set
14.2.1	Response – (RECIST v1.1) – Response Evaluable Analysis Set
14.2.2.1	Duration of Response (RECIST v1.1) – Response Evaluable Analysis Set
14.2.2.2	Duration of Response (RECIST v1.1) – KM – Response Evaluable Analysis Set
14.2.3.1	Duration of Stable Disease (RECIST v1.1) – Response Evaluable Analysis Set
14.2.3.2	Duration of Stable Disease (RECIST v1.1) – KM – Response Evaluable Analysis Set
14.2.4	Response – (iRECIST) – Response Evaluable Analysis Set
14.2.5.1	Duration of Response (iRECIST) – Response Evaluable Analysis Set
14.2.5.2	Duration of Response (iRECIST) – KM – Response Evaluable Analysis Set
14.2.6.1	Duration of Stable Disease (iRECIST) – Response Evaluable Analysis Set
14.2.6.2	Duration of Stable Disease (iRECIST) – KM – Response Evaluable Analysis Set
14.2.7	Progression Free Survival (RECIST) – KM – Response Evaluable Analysis Set
14.2.8	Progression Free Survival (iRECIST) – KM – Response Evaluable Analysis Set
14.2.9	Overall Survival – KM – Response Evaluable Analysis Set
14.3.1.1	Overall Summary of Treatment Emergent Adverse Events – Safety Analysis Set

Table Number	Table Title
14.3.1.2	Treatment Emergent Adverse Events by System Organ Class and Preferred Term – Safety Analysis Set
14.3.1.3	Treatment Emergent Adverse Events by System Organ Class, Preferred Term and Severity – Safety Analysis Set
14.3.1.4.1	Treatment Emergent Adverse Events Related to Etigilimab by System Organ Class and Preferred Term – Safety Analysis Set
14.3.1.4.2	Treatment Emergent Adverse Events Related to Nivolumab by System Organ Class and Preferred Term – Safety Analysis Set
14.3.1.4.3	Treatment Emergent Adverse Events Related to Etigilimab and Nivolumab by System Organ Class and Preferred Term – Safety Analysis Set
14.3.1.4.4	Treatment Emergent Adverse Events Related to Etigilimab or Nivolumab by System Organ Class and Preferred Term – Safety Analysis Set

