 Safety Analysis Set

System Organ Class Preferred Term [1]	Cohort A		Cohort B		Cohort E TMB-H/MSS	Cohort F Rare Tumors	Cohort G Post-CPI	Cohort H Ovarian	Total (N = XX)
	EC (N = XX)	n (%)	Head and Neck	Cervical					
System Organ Class 1									
Mild	X (XX.X)		X (XX.X)	X (XX.X)	X (XX.X)	X (XX.X)	X (XX.X)	X (XX.X)	X (XX.X)
Moderate	X (XX.X)		X (XX.X)	X (XX.X)	X (XX.X)	X (XX.X)	X (XX.X)	X (XX.X)	X (XX.X)
Severe	X (XX.X)		X (XX.X)	X (XX.X)	X (XX.X)	X (XX.X)	X (XX.X)	X (XX.X)	X (XX.X)
Preferred Term 1									
Mild	X (XX.X)		X (XX.X)	X (XX.X)	X (XX.X)	X (XX.X)	X (XX.X)	X (XX.X)	X (XX.X)
Moderate	X (XX.X)		X (XX.X)	X (XX.X)	X (XX.X)	X (XX.X)	X (XX.X)	X (XX.X)	X (XX.X)
Severe	X (XX.X)		X (XX.X)	X (XX.X)	X (XX.X)	X (XX.X)	X (XX.X)	X (XX.X)	X (XX.X)
Preferred Term 2									
Mild	X (XX.X)		X (XX.X)	X (XX.X)	X (XX.X)	X (XX.X)	X (XX.X)	X (XX.X)	X (XX.X)
Moderate	X (XX.X)		X (XX.X)	X (XX.X)	X (XX.X)	X (XX.X)	X (XX.X)	X (XX.X)	X (XX.X)
Severe	X (XX.X)		X (XX.X)	X (XX.X)	X (XX.X)	X (XX.X)	X (XX.X)	X (XX.X)	X (XX.X)

[1] MedDRA Version 26.0

TEAE = Treatment Emergent Adverse Event.

Note: A TEAE is an AE that emerges or worsens in the period from the first dose of study drug to 100 days after the last dose of study drug.

Note: Table shows distinct number of subjects with events for each system organ class/preferred term/severity.

Note: If a subject experienced a specific event more than once then the event with the worst severity is summarised.

Note: No subjects were recruited into Cohort D and so this cohort is not displayed.

Note: Percentages are based on the safety analysis set.

Source: Listing 16.2.7

Table 14.3.2.1
Haematology Parameters Summary
Safety Analysis Set

Parameter Visit	Cohort A EC CPI-Naïve (N = XX)		Cohort B Head and Neck (N = XX)		Cohort C Cervical (N = XX)		Cohort E TMB-H/MSS (N = XX)	
	Absolute	Change From Baseline	Absolute	Change From Baseline	Absolute	Change From Baseline	Absolute	Change From Baseline
RBC (10¹²/L)								
Baseline	n	X		X		X		X
	Mean (SD)	XX.X (XX.XX)		XX.X (XX.XX)		XX.X (XX.XX)		XX.X (XX.XX)
	Median	XX.X		XX.X		XX.X		XX.X
	Q1, Q3	XX.X, XX.X		XX.X, XX.X		XX.X, XX.X		XX.X, XX.X
	Min, Max	XX, XX		XX, XX		XX, XX		XX, XX
Day X	n	X	X	X	X	X	X	X
	Mean (SD)	XX.X (XX.XX)	XX.X (XX.XX)	XX.X (XX.XX)	XX.X (XX.XX)	XX.X (XX.XX)	XX.X (XX.XX)	XX.X (XX.XX)
	Median	XX.X	XX.X	XX.X	XX.X	XX.X	XX.X	XX.X
	Q1, Q3	XX.X, XX.X	XX.X, XX.X	XX.X, XX.X	XX.X, XX.X	XX.X, XX.X	XX.X, XX.X	XX.X, XX.X
	Min, Max	XX, XX	XX, XX	XX, XX	XX, XX	XX, XX	XX, XX	XX, XX

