Cohort/ Subject Number	MedDRA SOC / Preferred Term [1] / Adverse event (verbatim)	Start Date (Study Day) / Stop Date (Study Day)	TE [2] / TE_S [3] / NCI CTCAE Grade [4]	SAE / Serious Criteria [5]	Infusion Reaction? / Infection or Infestation?	AESI Infusion Immune	Related to: Etig/ Nivo/ Both	Outcome [6] / Action Taken Etig [7] / Nivo [7] / Other Action [8] /	Comments
XXX / XXXXX	XXXXXXXXX/ XXXXXX/ XXXXXX	DDMMYYYY (XX) / DDMMYYYY (XX)	Yes or No / Yes or No / X	Yes or No / XX	Yes or No / Yes, Yes COVID or No	Yes or No/ Yes or No	Related or Not Related/ Related or Not Related/ Related or Not Related	X / X / X / X	XXXXXXXXX XXXXXXXXX

NA = Not applicable, TE = Treatment Emergent, SAE = Serious Adverse Event, AESI = Adverse Event of Special Interest, NCI CTCAE = National Cancer Institute Common Terminology Criteria for Adverse Events (version 5.0).

[1] MedDRA Version 26.0.

[2] An AE occurring on or after the first dose of study drug and within 100 days of last dose of study drug.

[3] An AE occurring on or after the first dose of study drug, within 100 days of last dose of study drug and regardless of any other subsequent cancer treatment.

[4] Grade 1 = Mild, Grade 2 = Moderate, Grade 3 = Severe, Grade 4 = Life threatening, Grade 5 = Fatal.

[5] 1 = Death; 2 = Life-threatening; 3 = Hospitalization; 4 = Persistent or significant disability/incapacity; 5 = Congenital anomaly/birth defect; 6 = Other.

[6] Outcome: 1 = Resolved; 2 = Resolved with Minor Sequelae; 3 = Resolved with Major Sequelae; 4 = Ongoing; 5 = Fatal; 6 = Unknown.

[7] Action Taken: 1 = None; 2 = Dose held; 3 = Infusion interrupted; 4 = Drug permanently discontinued, 5 = Not applicable

[8] Other Action: 1 = None; 2 = Non-drug therapy given; 3 = Concomitant medication taken; 4 = Diagnostic procedure performed; 5 = Subject withdrawn; 6 = Subject hospitalized; 7 = Other.

Listing 16.2.8.1
Haematology

Cohort/ Subject Number	Visit	Collection Date (Study Day)	Parameter	Result	Change from Baseline	Units	Lower Limit	Upper Limit	Flag	Comments
XXXXX / XXXXX	XXX	DDMMYYYY (xx)	Basophils (abs)	X.XX	X.XX	X10 ⁹ /L	X.XX	X.XX	L / H	XXXXXXXXXXXX

Flag: L = below lower limit, H = above upper limit. # = Baseline.

Note: Values prefixed with < are treated as 0 when calculating the change from baseline.

Programming Note: The parameters should be listed in the order that they appear in the protocol.

Programming Note: # should be placed against the baseline measurement for each parameter.

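### The adverse event table by term and severity has no row for Grade 4 or 5, and the promised Grade 3-or-higher table by term is missing from the SAP's list of tables and shells

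*SAP*

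**What the plan says.** **Severity table.** Among the TEAE summaries, SAP 10.11.1 promises "Adverse Events by cohort, SOC, PT and severity". SAP 13.2 lists it as Table 14.3.1.3, "Treatment Emergent Adverse Events by System Organ Class, Preferred Term and Severity – Safety Analysis Set". Its shell in SAP 14 has three rows, mild, moderate and severe, under each organ class and each preferred term. Its footnotes read "Note: Table shows distinct number of subjects with events for each system organ class/preferred term/severity" and "If a subject experienced a specific event more than once then the event with the worst severity is summarised". SAP 10.11.1 gives the same counting rule: a repeated preferred term counts once, at the greatest severity observed.

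**Grade key.** The footnote to Listing 16.2.7 sets Grade 1 as mild, Grade 2 as moderate and Grade 3 as severe, followed by "Grade 4 = Life threatening, Grade 5 = Fatal". Protocol Appendix 4 has every event graded by CTCAE.

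**Overall summary.** SAP 10.11.1 describes this table as "also split by severity; mild, moderate, severe". Its shell, Table 14.3.1.1, instead has separate rows for Grades 1 to 5, all grades, Grade 3 or higher, and missing.

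**Grade 3 or higher.** SAP 10.11.1 also promises "Adverse Events of Grade 3 or Higher by cohort, SOC and PT". Protocol 9.3.2 makes the same commitment in the sentence that begins "Separate tabulations will also be produced for TEAEs assessed as related to study drug(s), TEAEs that led to treatment discontinuation" and goes on to name deaths and TEAEs of Grade 3 or higher; the synopsis in Appendix 9 repeats it.

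**Status of the lists.** SAP 10.1.2 says that Section 13 holds the full list of outputs for the final analysis and Section 14 their format and content. SAP 4 says that deviations from protocol-specified analyses are listed in Section 11.

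**The concern.** The shell for Table 14.3.1.3 counts each subject at worst severity on a scale that stops at Grade 3, while the events are graded on a scale that runs to Grade 5. Nothing in the SAP says what to do with a worst grade of 4 or 5.

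The Grade 3-or-higher table would cover part of that gap, because it would at least gather the serious end of the scale by term. It is promised in the text but appears in neither list that drives programming.

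Either defect alone would be partly covered by the other output. With both present, a reader of the tables cannot tell which preferred terms reached Grade 4, or how often each term reached Grade 3 or higher. Safety and tolerability of the combination is a secondary objective, and SAP 11 already states that laboratory toxicity grades will not be summarised, so the adverse event tables carry most of the grade information.

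**Working it through.** No sample size, power or error rate is involved. The check is a cross-match of text, list and shells.

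**Step 1. Rows against grades.**

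| CTCAE grade | Word in the Listing 16.2.7 key | Row in Table 14.3.1.3 | Row in Table 14.3.1.1 (not by term) |
|---|---|---|---|
| 1 | Mild | Yes | Yes |
| 2 | Moderate | Yes | Yes |
| 3 | Severe | Yes | Yes |
| 4 | Life threatening | None | Yes |
| 5 | Fatal | None | Yes |

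Three of the five grades have a row by term. No footnote or text merges Grades 4 and 5 into the severe row. Take a subject with one event of a given term at Grade 4:

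- If the rows follow the key, the subject appears in none of them, although Table 14.3.1.2 counts that subject for the term.
- If the subject is put under severe, that row mixes Grades 3, 4 and 5 and contradicts the key.

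Under neither reading does the table show that the term reached Grade 4.

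**Step 2. Tables promised in SAP 10.11.1.** Overall summary 1; by class and term 1; by severity 1; related 4; serious 1; serious and related 4; led to death 1; led to treatment discontinuation 1; led to study withdrawal 1; Grade 3 or higher 1; special interest 3; regardless of subsequent cancer treatment 2.

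1 + 1 + 1 + 4 + 1 + 4 + 1 + 1 + 1 + 1 + 3 + 2 = 21.

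**Step 3. Tables listed in SAP 13.2.** 14.3.1.1 to 14.3.1.3 (3); 14.3.1.4.1 to .4 (4); 14.3.1.5 (1); 14.3.1.6.1 to .4 (4); 14.3.1.7.1 to .3 (3); 14.3.1.8.1 to .3 (3); 14.3.1.9 (1); 14.3.1.10 (1).

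3 + 4 + 1 + 4 + 3 + 3 + 1 + 1 = 20.

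**Step 4. Tables covered by a shell in SAP 14.** Three own shells (14.3.1.1, 14.3.1.2, 14.3.1.3), one reuse of the first (14.3.1.9), and 16 reuses of the second.

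3 + 1 + 16 = 20.

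**Step 5. Match.** 21 − 20 = 1. Taken item by item, the unmatched table is Grade 3 or higher by class and term. It has no number, no shell and no place among the tables that reuse the 14.3.1.2 shell.

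**Step 6. Declared changes.** SAP 11 names two: the added TEAE definition and the absence of laboratory grade summaries. Dropping this table is not among them.

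**Step 7. What other outputs show.**

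| Output | Grade 4 by term | All Grade 3 or higher by term |
|---|---|---|
| 14.3.1.1 Overall summary | No: subject counts only | No: subject counts only |
| 14.3.1.2 All TEAEs by term | No: grade not shown | No: grade not shown |
| 14.3.1.5 Serious TEAEs by term | No: not split by grade | No: not split by grade, omits non-serious events |
| 14.3.1.7.3 TEAEs that led to death | No: deaths only | No: deaths only |
| Listing 16.2.7 | Per event, not tabulated | Per event, not tabulated |

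**The case against.** The best case against has four parts.

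**The overall summary does show Grades 4 and 5.** This is correct. The three-word split quoted from SAP 10.11.1 belongs to Table 14.3.1.1, whose shell has all five grades. The quoted text is out of step with its own shell, but that table hides nothing. The defect with consequences is in the 14.3.1.3 shell.

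**The events are not lost.** A reader might infer that every Grade 4 and 5 event disappears from the report by term. The documents do not support that. Table 14.3.1.7.3 gives TEAEs that led to death by term, Table 14.3.1.2 counts events of every grade by term, serious TEAEs are tabulated by term, and Listing 16.2.7 shows the grade of each event. What stands is narrower: no table isolates Grade 4, or Grade 3 and above, by term.

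**Exclusion is not established.** This also stands. The SAP never says that subjects at Grade 4 or 5 are left out of Table 14.3.1.3; a programmer could place them under severe. The supportable statement is that they have no assigned row and that both ways of proceeding are unsatisfactory.

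**The Grade 3-or-higher table is promised, so only a number and a shell are missing.** The SAP text does commit to it, and nothing shows a decision to drop it. But SAP 10.1.2 calls Section 13 the full list, so a team working from Sections 13 and 14 would not produce the table. That remains an inconsistency to repair.

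Two further inferences should be resisted. The earlier study's fatal TEAE rates (13.0% in Phase 1a, 20.0% in Phase 1b; Protocol 1.2) do not measure this gap, since deaths are the category that has its own table by term. And neither document promises a Grade 3-or-higher table by term limited to related events; its absence is not a defect.

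**Conclusion.** The point holds in two parts. The shell for Table 14.3.1.3 gives a row to three of five grades, so a worst grade of 4 or 5 has no defined place. One of 21 promised adverse event tables, the Grade 3-or-higher table by class and term that the protocol also specifies, is absent from the list and the shells, with no declared omission. In combination, no listed table identifies Grade 4 events, or all events of Grade 3 or higher, by preferred term.

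The consequence is modest but real. Safety reporting here is descriptive, and the information can be recovered from Listing 16.2.7 by hand. The number of subjects affected cannot be given from the documents, because it depends on how many reach Grade 4 or 5. The conclusion rests on two readings: that the Listing 16.2.7 key, the only mapping of grade to severity word in the SAP, also governs Table 14.3.1.3; and that Sections 13 and 14 define what will be produced, as SAP 10.1.2 says. It should be corrected before the tables are programmed.

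**What to change.** 1. In the Table 14.3.1.3 shell, replace the mild, moderate and severe rows with CTCAE Grades 1 to 5, keeping the worst-grade rule.
2. In SAP 10.11.1, replace the three-word severity split for the overall summary with Grades 1 to 5, to match the rows already in the Table 14.3.1.1 shell.
3. Add a numbered table of TEAEs of Grade 3 or higher by organ class and preferred term to SAP 13.2, and name it among the tables that reuse the 14.3.1.2 shell. If the sponsor does not intend to produce it, SAP 11 must say so as a departure from Protocol 9.3.2.

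The cost is one shell edit, one wording change and one extra table. The grade of each event is already in the adverse event data, as Listing 16.2.7 shows, so nothing new has to be collected.

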7.2. Secondary Endpoints

- Count and % of subjects who experience at least 1 adverse event (AE) and abnormal safety laboratory parameters
- Adverse events of special interest [(AESIs) infusion reactions, immune-related adverse events)]
- Relationship of PK and safety
- Disease control rate (DCR; is the proportion of subjects whose Best Overall Response is CR, PR, or SD)
- Duration of response (DoR)
- Duration of stable disease
- PK levels of etigilimab in combination with nivolumab
- Anti-drug antibodies (ADA) to etigilimab; Impact of developed etigilimab ADAs on PK levels of etigilimab

Note PK and ADA endpoints will not be evaluated as part of the analyses specified within this SAP.

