- Coagulation: prothrombin time (PT) (secs), activated partial thromboplastin time (APTT) (secs), International normalised ratio (INR).
- Thyroid Function Tests: Thyroid Stimulating Hormone (TSH), Free Triiodothyronine (T3), Free Thyroxine (T4).
- Other: β -HCG.
- Urinalysis: Specific gravity, pH, blood, glucose, protein, ketones.
- Urinalysis (microscopy): Urine RBC (/HPF), Urine WBC (/HPF), bacteria, casts and epithelial cells.

Laboratory data collected in different units to that shown will be converted to the above specified units (if possible) for presentation in subject Listings.

Summary statistics for absolute and changes from baseline by scheduled timepoint will be tabulated, by cohort, for haematology, biochemistry, thyroid function tests and coagulation. Baseline here will be the last non-missing measurements taken prior to the first infusion of etigilimab.

Laboratory parameters (Haematology, Biochemistry, Thyroid function tests, Coagulation, Urinalysis and Urinalysis (microscopy), where done) will be included in subject listings. Laboratory values outside the normal range will be identified in subject listings as above or below the normal range, and, where available, the CTCAE Toxicity Grade will be listed.

Unscheduled visit assessments will be included within subject listings.

10.11.3. *Vital Signs*

Vital signs will be measured at every visit throughout the trial. Specifically vital signs being measured prior to infusion of etigilimab, every 15 mins during the infusion and 30 and 60 mins after infusion for the first infusion with etigilimab. For subsequent infusions with etigilimab vital signs will be measured prior to infusion and 30 mins post-infusion.

Summary statistics for absolute and changes from baseline will be tabulated, by scheduled timepoint and by cohort, for vital signs parameters (systolic blood pressure (SBP) (mmHg), diastolic blood pressure (DBP) (mmHg), pulse rate (beats/min), respiratory rate (breaths/min), and temperature) and will be included within subject listings. Baseline vital signs are the last non-missing values taken prior to the first infusion with etigilimab.

10.11.4. *Physical Examination*

Any physical examination findings are reported as Adverse Events and will be listed there.

10.11.5. *ECOG Performance Status*

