Eastern Cooperative Oncology Group (ECOG) Performance is rated from Grade 0 to Grade 5, as per the table below. ECOG performance status will be summarised as a shift from the status at baseline and will also be listed.

10.11.6. *12-Lead ECG*

ECGs will be carried out at screening, 30 mins post-infusion on Cycle 1 Day 1, 30 mins post-infusion on Cycle 4 Day 1 and at treatment termination. Baseline will be the last non-missing results observed prior to infusion on Cycle 1 Day 1.

Summary statistics for absolute values and change from baseline by scheduled time point will be tabulated, by cohort and for all subjects, for ECG parameters (PR interval, QRS duration, QTc interval (sec) and QTcF interval (sec)).

10.11.7. *Contrast Enhanced Head CT or MRI Scan*

Any data collected for this test will be listed.

11.CHANGES TO THE PROTOCOL SPECIFIED ANALYSIS DETAILED IN THE STATISTICAL ANALYSIS PLAN

An additional definition of Treatment Emergent Adverse Event was added to the SAP:

Any adverse event that occurs after first dose of study treatment and within 100 days of last dose of study treatment regardless of whether they receive any subsequent cancer treatment between last dose of study drug and the adverse event.

Toxicity grades of laboratory parameters are not summarised.

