14.3.1.5	Serious Treatment Emergent Adverse Events by System Organ Class and Preferred Term – Safety Analysis Set
14.3.1.6.1	Serious Treatment Emergent Adverse Events Related to Etigilimab by System Organ Class and Preferred Term – Safety Analysis Set
14.3.1.6.2	Serious Treatment Emergent Adverse Events Related to Nivolumab by System Organ Class and Preferred Term – Safety Analysis Set
14.3.1.6.3	Serious Treatment Emergent Adverse Events Related to Etigilimab and Nivolumab by System Organ Class and Preferred Term – Safety Analysis Set
14.3.1.6.4	Serious Treatment Emergent Adverse Events Related to Etigilimab or Nivolumab by System Organ Class and Preferred Term – Safety Analysis Set
14.3.1.7.1	Treatment Emergent Adverse Events that Led to Treatment Discontinuation by System Organ Class and Preferred Term – Safety Analysis Set
14.3.1.7.2	Treatment Emergent Adverse Events that Led to Withdrawal from the Study by System Organ Class and Preferred Term – Safety Analysis Set
14.3.1.7.3	Treatment Emergent Adverse Events that Led to Death by System Organ Class and Preferred Term – Safety Analysis Set
14.3.1.8.1	Treatment Emergent Adverse Events of Special Interest (Infusion or Immune Related) by System Organ Class and Preferred Term – Safety Analysis Set
14.3.1.8.2	Treatment Emergent Adverse Events of Special Interest (Infusion Related) by System Organ Class and Preferred Term – Safety Analysis Set
14.3.1.8.3	Treatment Emergent Adverse Events of Special Interest (Immune Related) by System Organ Class and Preferred Term – Safety Analysis Set

Table Number	Table Title
14.3.1.9	Overall Summary of Treatment Emergent Adverse Events Regardless of Subsequent Cancer Treatment – Safety Analysis Set
14.3.1.10	Treatment Emergent Adverse Events Regardless of Subsequent Cancer Treatment by System Organ Class and Preferred Term – Safety Analysis Set
14.3.2.1	Haematology Parameters Summary – Safety Analysis Set
14.3.2.2	Biochemistry Parameters Summary – Safety Analysis Set
14.3.2.3	Coagulation Parameters Summary – Safety Analysis Set
14.3.2.4	Thyroid Function Parameters Summary – Safety Analysis Set
14.3.3	Vital Signs Parameters Summary – Safety Analysis Set
14.3.4	ECOG Performance Status – Shift from Baseline – Safety Analysis Set
14.3.5	Electrocardiogram Parameters Summary – Safety Analysis Set

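### The SAP keeps abnormal safety laboratory results in a secondary endpoint, but drops the protocol's CTCAE shift table and plans no table that counts affected subjects

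*SAP*

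**What the plan says.** SAP 7.2 carries the protocol's secondary safety endpoint over unchanged: "Count and % of subjects who experience at least 1 adverse event (AE) and abnormal safety laboratory parameters". The same section names the secondary endpoints that the SAP will leave out: "Note PK and ADA endpoints will not be evaluated as part of the analyses specified within this SAP". Laboratory abnormalities are not among them.

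For the analysis, Protocol 9.3.2 commits to the following: "A shift table, tabulation for baseline to each scheduled assessment and the worst post treatment value according to the CTCAE grade, will be provided". The sentence goes on to limit this to selected clinical laboratory tests, which it does not name.

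SAP Section 11, which records departures from the protocol's analysis, says "Toxicity grades of laboratory parameters are not summarised". SAP 10.11.2 describes what is tabulated instead: "Summary statistics for absolute and changes from baseline by scheduled timepoint will be tabulated, by cohort, for haematology, biochemistry, thyroid function tests and coagulation". Values outside the normal range are flagged in listings only, and "where available, the CTCAE Toxicity Grade will be listed".

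**The concern.** An endpoint defined as a count and percentage of subjects needs an output that counts subjects. The protocol's shift table was the output that came closest, because it classifies each subject by baseline grade and worst post-treatment grade. Once it is removed, the secondary endpoint is still declared but nothing in the table list delivers its laboratory part.

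For a combination of two checkpoint-directed antibodies, the useful safety question is how many subjects developed a graded laboratory abnormality and from what baseline. Protocol 1.2 reports the previous etigilimab study in that form. Grade 3 or higher results were most common for lymphocytes (8 of 23 subjects, 34.8%) and alkaline phosphatase (3 of 23, 13.0%) in Phase 1a, and for alkaline phosphatase (3 of 10, 30.0%) and AST (2 of 10, 20.0%) in Phase 1b. The outputs planned here could not be set beside those figures. Protocol 5.1 and 5.2 also tie dosing decisions to laboratory grade, so the protocol itself treats grade as a meaningful safety measure.

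**Working it through.** No formula applies. The check traces the endpoint from its definition to the planned outputs.

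1. **Definition.** Protocol Section 2 and SAP 7.2 use the same wording. The only exemptions in SAP 7.2 are PK and ADA, so the laboratory part remains in force.

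2. **Protocol analysis.** Protocol 9.3.2 specifies a grade shift table for selected tests, to each scheduled assessment and to the worst post-treatment value.

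3. **SAP change.** Section 11 removes summaries of laboratory grades. It gives no reason, does not mention the endpoint and names no substitute.

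4. **Planned laboratory tables.** SAP 13.2 lists four, Tables 14.3.2.1 to 14.3.2.4 (haematology, biochemistry, coagulation, thyroid function); the first is titled "Haematology Parameters Summary – Safety Analysis Set". They share one shell in SAP Section 14, with n, mean (SD), median, Q1 and Q3, and minimum and maximum, for the value and its change from baseline at each visit.

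5. **Tally.** Laboratory summary tables: 4. Laboratory shift tables: 0. Tables giving n (%) of subjects with an out-of-range or graded value: 0. The only shift table in the SAP, Table 14.3.4, is for ECOG performance status; the words Toxicity Grade in its column header do not make it a laboratory table.

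6. **Can the count be recovered from the four tables?** No. A raised maximum at a visit shows that at least one subject had a high value. A raised maximum at several visits may be one subject repeatedly or a different subject each time. Baseline grade is not linked to the later value at all.

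7. **Unscheduled results.** SAP 10.1.1 and 10.1.2 generally leave them out of summary tables unless the data review meeting decides otherwise. A worst value from an unscheduled draw can therefore be absent from all four tables. The protocol's shift was specified to the worst post-treatment value.

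8. **Listings.** SAP 10.11.2 promises the CTCAE grade where available. The shell for Listing 16.2.8.1, reused for biochemistry, coagulation and thyroid function, has a low/high flag and no grade column. As drafted, a laboratory grade appears in no laboratory shell.

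**The case against.** Several things count on the other side.

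**The change is declared.** SAP Section 4 says departures from the protocol will be listed in Section 11, and this one is. A reader might infer a concealed deviation; the documents do not support that. But declaring that grades are not summarised does not withdraw the endpoint in 7.2, and the two sections now disagree.

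**Adverse event tables cover much of the clinical question.** Protocol 8.3.6 sends clinically relevant laboratory changes to the adverse event page. Appendix 4 makes abnormalities judged clinically significant adverse events, graded by CTCAE. They then enter the tables by preferred term, by severity and by discontinuation, and Table 14.3.1.1 has grade rows. A reader might infer that severe hepatic or haematological toxicity would go unreported; that does not follow. What remains is that this route counts only what the investigator selects. Appendix 4 generally excludes findings tied to the underlying disease or its progression, which is a real restriction in metastatic cancer. SAP 10.11.1 also promises a Grade 3 or higher table by preferred term that is missing from the list in 13.2.

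**The laboratory shell is not limited to means and medians.** A large rise at a scheduled visit would show in the maximum and would move the mean and SD, so one cannot say that such rises would be invisible. They would be visible, but not countable.

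**Unscheduled values are not barred outright.** The data review meeting considers them subject by subject, and they are always listed. Scheduled haematology and chemistry are also frequent: Day 1 and Day 8 of each cycle through Cycle 6, then every two weeks.

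**The protocol promised less than full coverage.** Its shift table was for selected tests, and the endpoint says abnormal without a grade threshold. A table for every test in every panel would go beyond the commitment.

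**Conclusion.** The point stands as an unmet secondary endpoint. Of four planned laboratory tables, none gives the number or percentage of subjects with abnormal values, and the protocol's shift table has been removed without a reason or a replacement. The adverse event tables and the maxima reduce the clinical consequence but do not supply the missing result.

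This rests on two assumptions. The first is that count and percentage govern the laboratory clause as well as the adverse event clause, which is the natural reading. On a looser reading in which abnormal parameters merely have to be described, abnormality would still be shown only in listings. The second is that SAP 13.2 is the complete list of tables, as SAP 10.1.2 states.

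The prior-study rates show that graded laboratory abnormalities are not rare with this drug. They do not measure how much the omission would distort this report, and no such figure can be derived from the documents. The change should be made, but the primary endpoint does not depend on it.

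**What to change.** Replace the sentence in SAP Section 11 with a planned output, and list it in 13.2 with a shell:

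- a shift table from baseline CTCAE grade to worst post-treatment grade, using scheduled and unscheduled values, for the protocol's selected tests, which the SAP should name;
- n (%) of subjects with any abnormal value and with Grade 3 or higher, by cohort and in total, with abnormal defined (for example, outside the normal range).

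Add the CTCAE grade column promised in SAP 10.11.2 to the laboratory listing shell.

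If the sponsor decides against this, Section 11 should say that this part of the secondary endpoint will not be evaluated, and why. That would remove the contradiction with 7.2 but would not answer the safety question.

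The cost is a few extra tables and some grade derivation. A reader might assume the grades already exist for the listings. The documents do not establish that: grades are listed only where available, the shell has no column for them, tests are run at local laboratories (Protocol Appendix 2), and SAP 10.11.2 converts units only where possible. Limiting the table to the selected tests keeps the work small.
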